3.1 Treatment Cohort

Table 3-1 Study VX14-661-110: Treatment Cohort

Event/Assessment ^a	Day -28 to Day -1	Treatment Period ^b						ETT Visit/ Departing Visit (Within 7 Days of Last Dose of Study Drug) ^{b,c,d,e}	Safety Follow-up Visit 28 (± 7) Days After Last Dose ^{c,d,e}
		Day 1 ^f / Returning Visit ^{b,g}	Day 15 (± 3 days)	Weeks 8, 16, 24, 36 (± 5 days)	Week 48 (± 5 days)	Weeks 60, 72, 84 (± 5 days)	Week 96 (± 5 days)		
Clinic visit		X	X	X	X	X	X	X	X

^a All assessments will be performed before dosing unless noted otherwise.

^b Selected visits may overlap with visits in the other qualified Vertex study: the Screening Visit of the other qualified Vertex study and a scheduled Treatment Period visit; the last required visit of the other qualified Vertex study and the Returning Visit; and the visit with the first dose of study drug in the other qualified Vertex study and the ETT Visit (refer to [Section 8.1.1.1](#) and [Section 8.1.1.3](#) for the timing/order of assessments in these cases).

^c If the subject prematurely discontinues study treatment, an ETT Visit should be scheduled as soon as possible after the subject decides to terminate study treatment ([Section 8.1.1.3](#)). Subjects who prematurely discontinue treatment will also be required to complete the Safety Follow-up Visit, approximately 28 (± 7) days after their last dose of study drug. If the ETT Visit occurs 3 weeks or later following the last dose of study drug, then the ETT Visit will replace the Safety Follow-up Visit, and a separate Safety Follow-up Visit will not be required.

^d If a subject is continuing onto commercially available VX-661/ivacaftor, the ETT Visit ([Section 8.1.1.3](#)) will be completed before dosing with commercial drug begins, and the Safety Follow-up Visit ([Section 8.1.1.2](#)) will not be required.

^e If a subject discontinues treatment to participate in another qualified Vertex study, the ETT Visit ([Section 8.1.1.3](#)) will be completed, and the Safety Follow-up Visit ([Section 8.1.1.2](#)) will not be required if the subject enrolls in the other study within 28 (± 7) days of the last dose of study drug in Study VX14-661-110.

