8.1.1.2 Safety Follow-up

Treatment Cohort

Subjects who do not complete the Day 1 Visit in Study VX14-661-110 within 28 days after the last dose of study drug in the parent study are to complete the Safety Follow-Up Visit in the parent study before receiving the first dose of study drug in Study VX14-661-110.

The Safety Follow-up Visit is scheduled to occur 28 (\pm 7) days after the last dose of study drug. The Safety Follow-up Visit assessments are listed in [Table 3-1](#).

If a subject is continuing onto commercially available VX-661/ivacaftor, the Early Treatment Termination Visit ([Section 8.1.1.3](#)) will be completed before dosing with commercial drug begins, and the Safety Follow-up Visit will not be required.

If a subject discontinues treatment to participate in another qualified Vertex study, the Early Treatment Termination Visit ([Section 8.1.1.3](#)) will be completed, and the Safety Follow-up Visit will not be required if the subjects enrolls in the other study within 28 (\pm 7) days of the last dose of study drug in Study VX14-661-110.

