8.1.1.3 Early Treatment Termination

Treatment Cohort

If a subject prematurely discontinues study treatment, an Early Treatment Termination Visit should be scheduled as soon as possible after the subject decides to terminate study treatment and should occur within 7 days after the last dose of study drug. Subjects who prematurely discontinue treatment will also be required to complete the Safety Follow-up Visit, approximately 28 (\pm 7) days after their last dose of study drug as described in [Section 8.1.1.2](#). The assessments performed at the Safety Follow-up Visit are listed in [Table 3-1](#).

If the Early Treatment Termination Visit occurs 3 weeks or later following the last dose of study drug, then the Early Treatment Termination Visit will replace the Safety Follow-up Visit, and a separate Safety Follow-up Visit will not be required. If a subject discontinues Study VX14-661-110 to participate in another qualified Vertex study, and the subject does not re-enroll in Study VX14-661-110, the Early Treatment Termination Visit will replace the Safety Follow-up Visit, and a separate Safety Follow-up Visit will not be required.

During the course of study conduct, if VX-661 in combination with ivacaftor is approved and available for the treatment of CF in populations enrolled in Study VX14-661-110, subjects with

the approved *CFTR* genotypes may be discontinued from this rollover study at the discretion of the sponsor (Section 10.6). If a subject is continuing onto commercially available VX-661/ivacaftor, the Early Treatment Termination Visit will be completed before dosing with commercial drug begins, and the Safety Follow-up Visit (Section 8.1.1.2) will not be required. Alternatively, if local health authorities decline to approve, or if clinical benefit is not demonstrated for the use of VX-661 in combination with ivacaftor for the treatment of CF in populations enrolled in Study VX14-661-110, subjects with the relevant *CFTR* genotypes may be discontinued after communication to investigators and IRBs/IECs of the risks/benefits related to the safety and efficacy observed for the subset of subjects. If subjects are discontinued from the study, an Early Treatment Termination Visit should occur within 7 days of the last dose of study drug and a Safety Follow-up Visit should occur within 28 (\pm 7) days after the last dose of study drug.

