13.1.1.3 Documentation of Adverse Events

All AEs will be collected from the time ICF is signed, or assent, if applicable, until the following time points:

- Until time of withdrawal of consent
- For enrolled subjects who have a Safety Follow-up Visit: through the Safety Follow-up Visit
- For enrolled subjects who do not have a Safety Follow-up Visit, the **earliest** of:
 - 28 days after the last dose of study drug, or
 - the Early Treatment Termination Visit, if that visit is 3 weeks or later following the last dose of study drug (see [Section 8.1.1.3](#)), or

- the Early Treatment Termination Visit, or until the time of enrollment in another qualified Vertex study

All subjects will be queried, using non-leading questions, about the occurrence of AEs at each study visit. When possible, a constellation of signs and/or symptoms will be identified as 1 overall event or diagnosis. All AEs for enrolled subjects will be recorded in the eCRF and source document. The following data will be documented for each AE:

- Description of the event
- Classification of “serious” or “nonserious”
- Date of first occurrence and date of resolution (if applicable)
- Severity
- Causal relationship to study drug(s)
- Action taken
- Outcome
- Concomitant medication or other treatment given

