9 STATISTICAL ANALYSIS

9.1 General Considerations

Continuous variables will be summarized using the following descriptive summary statistics: the number of subjects (n), mean, standard deviation (SD), median, minimum value (min), and maximum value (max).

Categorical variables will be summarized using counts and percentages.

Visit Windowing Rules: [Section 11.1](#) defines the windows for protocol-defined visits. Note, spirometry assessments, BMI, weight, and height will be used for both efficacy and safety purposes. Their measurements will follow the visit windowing rules for efficacy parameters.

The windows will be applied for both scheduled and unscheduled visits. If no measurement is available within a visit window, the assessment will be considered missing for the visit. If there is more than one measurement available within the same visit window, the following rules will be used:

For all safety parameters, if there are multiple measurements within a visit window, then

- The record closest to the target day will be used, with the exception of the threshold analysis in which the worst record will be used.
- If there are multiple records within the same distance of the target day, the latest record will be used.
- The SFU visit will not be windowed; instead, the nominal visit will be used in relevant analyses.

For all efficacy parameters, if there are multiple measurements within a visit window, the record at the scheduled visit will be used. Otherwise,

- If there are multiple records with the same distance to the target day, the latest record will be used.
- If there are no measurements at the scheduled visit, then the record closest to the target day will be used.

- Assessments at the Early Treatment Termination (ETT) Visit will follow the windowing rules for regular visits.
- Assessments at SFU Visit will follow the windowing rules for regular visits if they fall within the upper boundary of the window for the last scheduled visit. If assessments occur after the upper boundary of the window for the last scheduled visit, they will be still considered as the SFU Visit.

Incomplete/Missing data will not be imputed, unless otherwise specified.

Outliers: No formal statistical analyses will be performed to detect or remedy the presence of statistical outliers, unless otherwise specified.

Unscheduled **Visits:** Unscheduled visit measurements will be included in the following:

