- Derivations of measurements at scheduled visits per specified visit windowing rules;
- Derivations of baseline/last on-treatment measurements;
- Derivations of the maximum/minimum on-treatment values and maximum/minimum changes from baseline values for safety analyses;
- Data listings where appropriate.

Treatment-emergent (TE) Period will include the time from the first active dose of VX-661/ivacaftor or ivacaftor alone (in the parent study or Study VX14-661-110, but after the washout period, if applicable) to the Safety Follow-up Visit in Part A or 28 days after the last dose of the study drug for subjects who do not have a Safety Follow-up Visit or who have their Safety Follow-up Visit more than 35 days after the last dose in Part A of Study VX14-661-110. For subjects who participate in another qualified Vertex study before completing Part A of Study VX14-661-110 (96 weeks) and re-enroll in Study VX14-661-110, the TE Period will exclude the time spent in the other study.

110 Treatment-Emergent (TE) Period is defined as the time from 1st dose of study drug in Part A to SFU in Part A or 28 days after the last dose of the study drug for subjects who do not have a SFU Visit or who have their SFU Visit more than 35 days after the last dose in Part A. For subjects who participate in another qualified Vertex study before completing Part A (96 weeks) and re-enroll in Study 110, the TE Period will exclude the time spent in the other study. The **efficacy analysis baseline** is defined as the most recent non-missing measurement (scheduled or unscheduled) collected prior to the first dose of study drug in the parent studies for all subjects, except for subjects randomized to the placebo arm in Study 106.

The efficacy analysis baseline for subjects randomized to the Study 106 placebo arm is defined as the most recent non-missing measurement (scheduled or unscheduled) collected prior to the first dose of study drug in Study 110.

The **safety analysis baseline**, unless otherwise specified, is defined as the last non-missing assessment prior to the first dose of active treatment (TEZ/IVA or IVA) from the parent study (after the wash-out period, where applicable) or Study 110, whichever is earlier.

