11 APPENDICES

11.1 Analysis Visit Window Mapping Rules

Table 11-1 Visit Window Mapping Rules for Safety Measurements

Assessments	Visit	Target Study Day	Visit Window (in study days)

 • Standard 12-lead ECG • Vital signs • Pulse oximetry • Labs 
 ○ Chemistry ○ Hematology 	Day 1	1	[1, 1]
	Day 15	15	[2, 36]
	Week 8	57	[37, 85]
	Week 16	113	[86, 141]
	Week 24	169	[142, 211]
	Week 36	253	[212, 295]
	Week 48	337	[296, 379]
	Week 60	421	[380, 463]
	Week 72	505	[464, 547]
	Week 84	589	[548, 631]
	Week 96	673	[632, 687]
	ETT	N/A	Follow the individual visit window to be mapped to individual visits
Safety Follow-up Visit	N/A	Nominal (remain as SFU)	

 • Coagulation • Lipid Panel • Labs 
 ○ Vitamin Level ○ Urinalysis 	Day 1	1	[1, 1]
	Week 8	57	[2, 85]
	Week 16	113	[86, 141]
	Week 24	169	[142, 211]
	Week 36	253	[212, 295]
	Week 48	337	[296, 379]
	Week 60	421	[380, 463]
	Week 72	505	[464, 547]
	Week 84	589	[548, 631]
	Week 96	673	[632, 687]
	ETT	N/A	Follow the individual visit window to be mapped to individual visits
	Safety Follow-up Visit	N/A	Nominal (remain as SFU)

Note: spirometry assessments, BMI, weight, and height will be used for both efficacy and safety purposes. Their measurements will follow the visit windowing rules for efficacy measurements.

Table 11-2 Visit Window Mapping Rules for Efficacy Measurements

Assessments	Visit	Analysis Visit	Target Study Day	Visit Window (in study days)

 • Spirometry • CFQ-R 	Day 15	Study 110 Day 15	15	[2, 36]
	Week 8	Study 110 Week 8	57	[37, 85]
	Week 16	Study 110 Week 16	113	[86, 141]
	Week 24	Study 110 Week 24	169	[142, 211]
	Week 36	Study 110 Week 36	253	[212, 295]
	Week 48	Study 110 Week 48	337	[296, 379]
	Week 60	Study 110 Week 60	421	[380, 463]
	Week 72	Study 110 Week 72	505	[464, 547]
	Week 84	Study 110 Week 84	589	[548, 631]
	Week 96	Study 110 Week 96	673	[632, 687]
	ETT		N/A	Follow the individual visit window to be mapped to individual visits
Safety Follow-up Visit	Safety Follow-up Visit	N/A	Follow the individual visit window to be mapped to individual visits if fall within the upper boundary of the window for the last scheduled visit (Day 687); or remain as SFU if otherwise.	

 • Weight and height • BMI 	Week 8	Study 110 Week 8	57	[2, 85]
	Week 16	Study 110 Week 16	113	[86, 141]

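### An ETT Visit held 21 or more days after the last dose replaces the Safety Follow-up Visit, but the SAP recognises that visit by name only and windows the ETT safety data into a Treatment Period visit

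*Protocol*

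**What the plan says.** **Protocol.** Table 3-1 footnote c states that an ETT Visit which "occurs 3 weeks or later following the last dose of study drug, then the ETT Visit will replace the Safety Follow-up Visit". Section 8.1.1.3 says the same: "then the Early Treatment Termination Visit will replace the Safety Follow-up Visit, and a separate Safety Follow-up Visit will not be required". In Section 8.1.1.2, "The Safety Follow-up Visit is scheduled to occur 28" (± 7) days after the last dose, that is, on days 21 to 35. Table 3-1 schedules the same laboratory panels, ECG, vital signs and oximetry at both visits.

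**SAP, visit assignment.** For safety parameters Section 9.1 says: "The SFU visit will not be windowed; instead, the nominal visit will be used in relevant analyses". In Table 11-1 the ETT row reads "Follow the individual visit window to be mapped to individual visits", with no condition on time since the last dose. The notes in Section 11.1 have the SFU labelled from its nominal name first, and then window everything that remains. Within a window, the record closest to the target day represents the visit. Threshold analyses use the worst record instead.

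**SAP, analysis period.** The 110 Treatment-Emergent (TE) Period runs to the SFU if that is held within 35 days. Otherwise it ends "28 days after the last dose of the study drug for subjects who do not have a SFU Visit" or whose SFU came later than that. Sections 9.7.2 to 9.7.5 limit the laboratory, ECG, vital-sign and oximetry summaries to this period.

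**The concern.** The 3-week threshold is where the SFU window opens (28 − 7 = 21 days). A late ETT therefore does the SFU's work, with the same measurements on the same post-dose days. The SAP nevertheless treats the two differently because of the visit name. The off-drug ETT value enters a Treatment Period row, and the SFU row loses that subject.

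The outputs at stake serve the primary objective, long-term safety. They are the by-visit values and changes from baseline, the mean plots of liver function tests, and the by-visit shift tables. The affected subjects are early stoppers, whose off-drug values may differ from their on-drug values.

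**Working it through.** The plan gives no figure to reproduce, so the check applies its rules to dated examples.

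**Inputs.**
- Safety windows from SAP Table 11-1: Week 36 is [212, 295] with target Day 253, and Week 96 is [632, 687]. The windows are contiguous from Day 2 to Day 687.
- Replacement from day 21 after the last dose: Protocol Table 3-1 footnote c.
- TE end from SAP 9.1: the SFU date if within 35 days of the last dose, otherwise last dose + 28.

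**Example 1: gap of 21 to 28 days.** Last dose Day 230, an on-drug unscheduled chemistry on Day 228, ETT on Day 254.
- Time off drug: 254 − 230 = 24 days. TE end: 230 + 28 = Day 258, so the record is inside the period.
- Distance from target: |254 − 253| = 1 day for the ETT, and |228 − 253| = 25 days for the on-drug record.
- The off-drug ETT represents Week 36. Without the Day 228 record, the ETT would be the only value in the window and would fill the row anyway.
- Labelled SFU, the Day 254 record goes to the SFU row and the Day 228 record represents Week 36.

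**Example 2: gap of 29 to 35 days.** Same last dose, ETT on Day 260.
- Time off drug: 260 − 230 = 30 days. If the subject counts as having no SFU, the period ended on Day 258, so the measurements are in no TE-limited summary.
- A nominal SFU on Day 260 would be included, since 30 ≤ 35.

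**Example 3: past the last window.** Last dose Day 664, ETT on Day 689 (25 days). This is inside the TE Period (664 + 28 = Day 692) but beyond Day 687, so it has no by-visit row. Labelled SFU, it would have one.

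**All rule combinations, last dose on Days 1 to 671.**

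| Gap (days) | Combinations | Labelled ETT (no SFU) | Labelled SFU |
|---|---|---|---|
| 21–28 | 671 × 8 = 5,368 | 5,300 (98.7%) to a scheduled visit; 68 (1.3%) past Day 687 | all in the SFU row |
| 29–35 | 671 × 7 = 4,697 | all outside the TE Period | all in the SFU row |
| 36–42 | 671 × 7 = 4,697 | all outside | all outside |

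For last doses on Days 2 to 671 and gaps of 21 to 28 days, 1,764 of 5,292 mapped combinations (33.3%) land in a later window than the one holding the last dose. These are counts of rule combinations, not expected shares of subjects.

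**Which outputs change at gaps of 21 to 28 days.** By-visit means and plots change when the late ETT is the only record in the window or the closest to target. If the by-visit shift tables follow the worst-record rule, they change only when the late ETT is the only or the worst record. Whole-period threshold counts do not change, because the record is inside the period under either label.

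**Size.** If k of the n records in a row are late ETTs and d is the mean off-drug minus on-drug difference, the row mean moves by (k/n) × d. The documents give neither k nor d. Assume k from 1 to 20. With n = 1,044 (all enrolled, SAP 6.2) the factor k/n is 0.1% to 1.9%. With n = 1,044 − 159 − 138 = 747 (without Studies 107 and 109) it is 0.1% to 2.7%.

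**The case against.** **A late ETT does not become the SFU in every respect.** The protocol says it replaces that visit. Section 13.1.1.3 places "the Early Treatment Termination Visit, if that visit is 3 weeks or later following the last dose of study drug" among the end points for subjects who do not have an SFU, and stops adverse-event (AE) collection at the earliest of the listed times, so by day 28. Protocol 12.3.1 sets the same 28-day end of the TE Period as the SAP. This stands. A reader might infer that the SAP ends the TE Period wrongly and loses adverse events after day 28, but the documents do not support that. Extending the period would add days on which AEs were no longer being collected.

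**The loss on days 29 to 35 depends on the reading.** The name-only rule governs windowing. The TE definition does not say that its SFU must be nominal. This also stands, and it is a reason to state the rule.

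**Off-drug values in TE summaries are not a breach.** The period includes up to 28 days off drug by design, or 35 with an SFU. Unscheduled monitoring after stopping is windowed too, so the correction would not clear every off-drug value from the rows. True, but the SAP chose to keep the SFU out of those rows, and it applies that choice unevenly.

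**Abnormalities are not hidden.** Threshold counts use the worst record, and out-of-range laboratory values are listed. This stands, so a reading that safety signals in early stoppers are lost goes too far.

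**Late ETTs should be uncommon.** The visit is due within 7 days of the last dose. A reader might infer from footnotes b and e that late ETTs are routine for subjects moving to another study. Footnote b permits a shared visit day, and footnote e times enrolment in the other study, not the ETT. Nor do the 159 + 138 = 297 subjects from Studies 107 and 109, discontinued early according to SAP 7.1, give a count of late ETTs.

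**The database may already use the SFU name for such visits.** Then nothing goes wrong, but neither document says so.

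**Conclusion.** The mismatch is real and narrow. Under the SAP as written, measured safety data from an ETT 21 to 28 days after the last dose can represent a Treatment Period visit, while an SFU on the same day is reported separately. The effect is confined to descriptive by-visit means, liver-test plots and shift tables. For days 29 to 35 there is a smaller gap, since the measurements drop out of the TE-limited summaries if the subject is held to have no SFU.

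The conclusion assumes that a replacing ETT keeps the ETT name in the database. The number of such visits is not given and is probably small, so the numerical effect is likely to be slight. The case for the change is that it is cheap and carries a stated protocol rule into the SAP. The point does not extend to adverse-event counts, nor to efficacy, where SFU and ETT data are both windowed up to Day 687.

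**What to change.** 1. In SAP 9.1 and Table 11-1, state that for measured safety data (laboratory, ECG, vital signs, oximetry) an ETT held 21 or more days after the last dose is analysed in the SFU row and not windowed.
2. Include such a record in the SFU row up to day 35, as for a nominal SFU. Leave the TE Period for adverse events unchanged, and reconcile the wording with Protocol 13.1.1.3. State also whether records from days 29 to 35 enter the whole-period threshold counts.
3. Key the flag to time since the last dose, not to whether the SFU was replaced. Section 8.1.1.3 also lets the ETT replace the SFU, with no time condition, for subjects who leave for another qualified study and do not re-enrol.
4. State how the database names an ETT that replaced the SFU, and report the number of such visits.

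The cost is one sentence and a flag derived from the last-dose and visit dates, both already collected. The one side effect is that measured data for these subjects may run up to 35 − 28 = 7 days beyond their AE period, which a table footnote should say.

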3.2 Observational Cohort

Table 3-2 Study VX14-661-110: Observational Cohort

Event/Assessment	Day 1 ^a	Long-term Follow-up	
		Approx. Every 3 to 4 Months for the First Year	Approx. 2 Years (± 4 weeks)
Clinic visit	X		
Telephone contact		X	X
Informed consent/assent	X		
Inclusion criteria review ^b	X		
Related serious adverse events	Continuous from signing of ICF and Assent through last telephone contact		

ICF: informed consent form.

^a The Day 1 Visit of Study VX14-661-110 will be on the **same day** as the last scheduled visit of the parent study for subjects at Study VX14-661-110 sites that have been activated by the time the subject has completed the last visit in the parent study. Subjects at these active sites will **NOT** have to repeat any Study VX14-661-110 Day 1 assessments that were specified to be performed at the last scheduled visit of the parent study. However, the Day 1 Visit of Study VX14-661-110 **will NOT coincide** with the last scheduled visit of the parent study for subjects at Study VX14-661-110 sites that have NOT been activated by the time the subject has completed the last scheduled visit in the parent study. Subjects at these nonactive sites will have to repeat any Study VX14-661-110 Day 1 assessments that were specified to be performed at the last scheduled visit in the parent study.

^b Subjects must be < 18 years of age (age on the date of informed consent/assent in the parent study) and meet the other inclusion criteria (Section 9.1) to be eligible for the Observational Cohort.

